#### IRB # 38115 Version: December 28, 2018

We will use the clinical trial data to determine whether the everolimus approach is cost-effective relative to the calcineurin inhibitor based regimen. Costs will be estimated from the perspective of the provider and the time horizon will cover the period of the trial. Costs will be obtained from the hospital's cost-accounting database and will include fixed and variable direct medical costs. Our effectiveness measure for the base case analysis will be renal function either as a continuous measure or in categorical increments (e.g. 5 or 10 ml/min). As a secondary measure of effectiveness we may also study life years gained (YLG), but only if substantial differences are observed in the sample. This will be estimated by the area under the survivor functions for each treatment arm.

Cost-effectiveness analysis asks whether one intervention provides value for resources expended compared to another intervention and is appropriate when alternative interventions have differing implications for costs and patient outcomes. The cost-effectiveness of the everolimus strategy will be summarized with an incremental cost-effectiveness ratio (ICER).

$$ICER = \frac{C_e - C_{ci}}{E_e - E_{ci}} \tag{1}$$

[figure not shown]
where  $C_e$  the cost of the everolimus strategy,  $C_{ic}$  is the cost of the calcineurin inhibitor strategy,  $E_e$  is the effectiveness of the everolimus strategy, and  $E_{ci}$  is the effectiveness of the calcineurin inhibitor strategy. Although we are interested in YLG gained as a measure of effectiveness it is not likely that with 24 patients the difference will be substantial enough to use. Therefore, our primary measure of effectiveness will be units of improvement in renal function. As a secondary measure we will use YLG if large enough differences are observed in our sample. The ICER represents the incremental cost required to achieve one additional unit of benefit if patients are transtioned from cacineurin inhibitors to everolimus. The uncertainty surrounding the ICER estimates will be quantified by bootstrapping our cost and effectiveness data to form 95% ellipses around the cost-effectiveness ratio[25-27]. We will also estimate cost-effectiveness acceptability curves to show how the likelihood of cost-effectiveness varies with the willingness to pay of the decision maker [28].

For all statistical analyses we will define significance as p-values less than 0.05. If multiple comparisons are required (for example, to study the same variable at difference time points) then we will adjust the p-values using a Bonferroni correction.

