### Protocol

Version: December 28, 2018

Randomization will only occur between 90days and 120 days post transplant. Patients randomized between 90 days and 120 days for conversion to Everolimus, in association with Mycophenolic acid, will start Everolimus at a dose of 0.75mg twice daily, with target levels at 3 to 8 ng/mL. Blood levels of Everolimus will be measured by the FDA approved assay by ThermoFisher. The calcineurin inhibitor (tacrolimus or cyclosporine) will be withdrawn after the target levels of Everolimus are reached.Concurrent immunosuppression with MPA will be maintained in both arms with dosage dependant on the degree of bone marrow suppression and leucopenia.

The calcineurin inhibitor (tacrolimus or cyclosporine) will be withdrawn after the target level of Everolimus is reached.

For Tacrolimus: After everolimus blood trough levels have been confirmed to be in the target range (3-8 ng/mL), tacrolimus tapering will begin, targeting a tacrolimus whole blood trough level of 3-5 ng/mL by three weeks after randomization. Once that point is reached tacrolimus elimination will begin while maintaining everolimus whole blood trough levels within the target range of 6-8 ng/mL.

For Cyclosporine: After everolimus blood trough levels have been confirmed to be in the target range (3-8 ng/mL), cyclosporine tapering will begin, targeting a cyclosporine whole blood trough level of 50 to 100 ng/mL by three weeks after randomization. Once that point is reached cyclosporine elimination will begin while maintaining everolimus whole blood trough levels within the target range of 6-8 ng/mL.

Prior to CNI elimination, the inclusion criteria for liver function tests will be re-applied. If a patient does not exhibit a functioning allograft at an acceptable level by as defined by the AST, ALT, Total Bilirubin levels being ≤3 times the upper limits of the normal values (ULN) and Alkaline Phosphatase and Gamma Glutamyl Transferase levels ≤5 times ULN, then the patient will be monitored until these criteria are met, after which tacrolimus/cyclosporine elimination can begin.

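### Life-years gained will be used only if the observed difference is large, so a reported value will on average be too far from zero

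*Combined protocol and SAP*

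**What the plan says.** Section 11.0 makes renal function the main effectiveness measure for the incremental cost-effectiveness ratio (ICER) and life-years gained a secondary one. The condition on YLG appears twice. First: "we may also study life years gained (YLG), but only if substantial differences are observed in the sample". Then, after the ICER formula: "As a secondary measure we will use YLG if large enough differences are observed in our sample". Between the two, the authors say of the YLG difference that "it is not likely that with 24 patients the difference will be substantial enough to use".

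On the estimator, the plan says: "This will be estimated by the area under the survivor functions for each treatment arm". On the horizon: "the time horizon will cover the period of the trial". Uncertainty in the ICER is to come from bootstrapping the cost and effectiveness data, with acceptability curves.

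The plan does not say how large is large enough, on what scale or in which direction, or who decides. It makes no allowance for the selection. Separately, Section 11.0 compares patient and graft survival by Kaplan-Meier curves and the log-rank test, with no condition on size.

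**The concern.** The rule decides whether to report an estimate by looking at that estimate. Small differences are left out and large ones go forward to an ICER. The average of what gets reported is then further from zero than the true difference, even though the estimator itself is unbiased.

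The problem is sharpest when sampling error is large relative to any plausible effect. That is the case here: there are 12 patients per arm, and the authors themselves doubt that a usable difference will appear. If one does appear, chance is a leading explanation.

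The YLG difference is the denominator of the ICER. If everolimus costs more and the selected difference favours it, the cost per life-year will look too low. If the selected difference goes the other way, everolimus will look worse than it is. The bootstrap resamples the data that passed the filter, so its results centre on the selected estimate and do not reflect the filter.

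**Working it through.** **Inputs from the documents**
- 12 per arm, 24 in total (Sections 4.0 and 11.0).
- Start of follow-up: "Randomization will only occur between 90days and 120 days post transplant" (Section 6.0).
- End of follow-up: the month 24 visit post transplant (Section 6.0 evaluation schedule). Taking randomization at about 3.5 months, follow-up is 24 - 3.5 = 20.5 months, so L = 20.5/12 = 1.708 years.
- Estimator: difference in area under the survivor functions. Without loss to follow-up this is the difference in mean min(T, L).

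**The plan's own figure.** None is given for YLG. The stated sample size does reproduce: a two-group t-test with difference 9.0, SD 7.5, two-sided 0.05 and 80% power gives n = 11.94, so 12 per group (power 80.2%). With SD 16 it gives 50.59, so 51. That calculation is for renal function and says nothing about survival.

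**How coarse the estimate is.** A death at time t lowers an arm's mean by (L - t)/12. One death halfway through follow-up costs (1.708/2)/12 = 0.071 years. One death at the very start costs 1.708/12 = 0.142 years. A single extra mid-period death therefore passes a 0.05-year cut-off, and two extra such deaths (0.142) almost reach 0.15.

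**Assumptions that the documents do not supply.** Two-year mortality of 10% or 20% in Arm B, exponential survival, no loss to follow-up, cut-offs c of 0.05, 0.15 and 0.30 years, and reporting when |difference| ≥ c, because the rule names no direction.

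**True gain if the Arm A hazard is halved.** Hazard h = -ln(1 - m)/2, and restricted mean = (1 - exp(-hL))/h.
- m = 10%: h = 0.0527. Arm B 1.6337, Arm A 1.6705, gain 0.0368 years.
- m = 20%: h = 0.1116. Arm B 1.5554, Arm A 1.6295, gain 0.0741 years.

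**Simulation, 400,000 trials per scenario.** Each cell gives the result at 10% and then 20% mortality.

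| Cut-off (years) | No true difference: share of trials reporting YLG | Hazard halved: mean reported gain / true gain |
|---|---|---|
| 0.05 | 62%, 74% | 1.7, 1.3 |
| 0.15 | 17%, 34% | 3.9, 2.4 |
| 0.30 | 2%, 6% | 8.0, 4.4 |

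At c = 0.15 with no true difference, the mean absolute reported difference is 0.22 and 0.24 years. With the hazard halved, the mean reported gain is 0.145 (true 0.037) and 0.177 (true 0.074).

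**Other survival assumptions** (survival at the end of 1.7 years, Arm A vs Arm B)
- 95% vs 85%, true gain 0.088: mean reported 0.159 (1.8 times) at c = 0.1 and 0.255 (2.9 times) at c = 0.2.
- 95% vs 90%, true gain 0.044: 2.3 and 4.4 times, with the wrong sign in 23% and 14% of reported results.
- 97% vs 80%, true gain 0.151: 1.4 and 2.0 times.
- 99% vs 60%, true gain 0.360: 1.04 and 1.12 times.

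**Without the filter.** When every trial reports, the mean estimate equals the truth: 0.088 against 0.088 for 95% vs 85%, and 0.000 against 0 for 90% vs 90%.

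**The case against.** The best defence is that little depends on this. YLG is a secondary measure within a secondary objective of a pilot, and the authors say they do not expect to use it. The unconditional Kaplan-Meier and log-rank analysis lets a reader see the survival data behind any YLG figure. This stands and limits the consequence, but it does not correct a published cost per life-year.

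The second defence is that the size rests on invented inputs. This also stands. The cut-off matters most and the plan gives none, so the multiples illustrate the rule and are not properties of the trial.

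A reader might also infer more than the documents support:
- *Every reported value is inflated.* The inflation is an average over reported results. A particular estimate must exceed the truth in size only if the cut-off does, and the effect nearly vanishes when the true difference is far above the cut-off (1.00 to 1.03 times for 99% vs 40% survival).
- *The rule favours everolimus.* No direction is stated. With no true difference, the signed mean of reported results is about zero. Counting only differences of at least 0.15 years in favour of everolimus would give 3.3 to 6.0 times the truth with the hazard halved, but the plan does not say that reporting is one-sided.
- *The base-case measure is exposed in the same way*, because it is "renal function either as a continuous measure or in categorical increments (e.g. 5 or 10 ml/min"). The increments may only set the unit of the ratio, as in cost per 5 or 10 mL/min, which is a rescaling with no inferential effect. Nothing there ties the choice to the result, so it is not part of this point.

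**Conclusion.** The concern holds as an average statement. As written, the plan selects the YLG difference on its own size, and the reported difference is expected to be too far from zero in either direction. Bootstrapping the selected data leaves this in place.

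Under the stated assumptions, a halved hazard would be reported at about 1.3 to 8 times its true gain over cut-offs of 0.05 to 0.30 years. With no true difference, YLG would still be reported in anywhere from about 2% to 74% of trials. These ranges depend on assumed mortality, exponential survival, complete follow-up and two-sided reporting.

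The primary endpoint, the renal ICER and the survival comparison are not affected. This is a minor point that is worth correcting because the correction is free.

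**What to change.** In the cost-effectiveness part of Section 11.0, delete both conditions: "but only if substantial differences are observed in the sample" and the matching clause in "As a secondary measure we will use YLG if large enough differences are observed in our sample". Then choose one of two options in advance:

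1. State that the difference in restricted mean survival from randomization to month 24 post transplant will be reported with its bootstrap interval whatever its size or direction, and that any cost per life-year will be shown beside it.
2. Drop YLG and say that 24 patients are too few for it to be informative.

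Either option costs only a wording change. The survival data and the bootstrap are already planned, and no patients, visits or assessments are added.

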#### Protocol

Version: December 28, 2018

Visit number	1 Screening*	2 Baseline*	3	4	5
Time of Visit	90days-120 days post transplant	90days- 120 days post transplan t	Month 6 +/- 2 weeks***	Month 12 +/- 2 weeks ***	Month 24 +/- 2 weeks ***
Inclusion/Exclusion criteria	Х	Х			
Informed consent	Х				
Physical examination(medical history and vital signs	Х	Х	х	х	Х
Clinical assessment	Х	Х	Х	Х	Х
Quality of Life Questionnaires (FACT-Hep; EQ-5D)	Х	Х	Х	Х	Х
Dispense study medication		Х			
Return study medication					х
Laboratory test (blood & urine collection)	Х	Х	Х	Х	Х
Adverse events		Х	Х	Х	х
Blood test-HIV, hepatitis viruses, CMV and genotyping	Х				
Pregnancy Test	Х				
Concomitant Medications (Standard of Care) **					
Valcyte	Х	Х			
Bactrim(PCP prophylaxis)	Х	Х	Х	Х	
Mycophenolic acid (Myfortic)	Х	Х	Х	Х	Х

\* If the patient meets all inclusion criteria at the Screening Visit, the Screening and Baseline visits may occur on the same day and will occur between 90 days and 120 days post transplant.

\*\*All patients receive CMV prophylaxis with Valcyte in the 1st 4 postoperative months as part of standard care. Bactrim prophylaxis against Pneumocystis carinii is administered for the first year post transplant as part of standard care. Steroids are discontinued at 3 months post-transplant while Myfortic is continued as part of the maintenance immunosuppressive protocol.

\*\*\*Visit window for follow up visits at months 6, 12 and 24 is plus or minus 2 weeks

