#### Tests at above evaluation schedule:

- a. Renal function as assessed by the iothalamate clearance test starting at Baseline visit.
- b. Renal Function as assessed by serum creatinine, by Cockcroft-Gault formula mL/min, and 24 hour urine collection for creatinine clearance and urinary protein level starting at Baseline visit.
- c. Liver Recipient blood sample for genotype testing.
- d. Testosterone levels

The genetic tests will involve TaqMan real-time PCR of extracted DNA, and subsequent identification of alleles associated with investigated polymorphic SNP by means of allele-specific 5' nuclease assay, using the pre-developed assay and Custom TaqMan® SNP Genotyping reagents for allelic discrimination by TaqMan real-time PCR on AbiPrism 7900HT Sequence Detection System (Applied Biosystems, Foster City, CA). The above will involve following genes and polymorphisms: CYP3A5

#### Amendment 6Page 8 of 18

IRB # 38115 Version: December 28, 2018

gene: 6986 A>G (alleles \*1 and \*3) and ABCB1 (MDR1) exon26 (3435C>T) and exon21 (2677G>T/A).

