# **11.0** Statistical Analysis of the Study

The primary endpoint of the trial is a renal function as assessed by 24 hour creatinine clearance.

We will compare creatinine clearance between the two arms of the study using a t-test. We expect that due to randomization there will be no differences in baseline characteristics of the two groups, so no multivariate analyses are planned. However, if we find significant difference between the two groups in such variables as demographics or disease characteristics, we will control for these variables in a linear regression analysis. In addition, we will also explore the use of nonparametric tests (i.e. Mann-Whitney U test for renal function) because of the relatively small sample size.

Secondary endpoints will also be tested using univariate statistical tests. The presence of acute rejection will be compared between study arms using chi-square tests. We will also fit nonparametric survival models to the time to acute rejection to determine whether rejection occurs earlier or later between study arms. Patient and graft survival will be modeled using Kaplan-Meier curves, with comparisons made between arms using the log rank test. To study the effect of donor and recipient genotype testing on postoperative renal function we will study the interaction between treatment arm and presence of CYP3A and P-gp SNPs on creatinine clearance. This will be done using a one-way analysis of variance with main effects for treatment and SNPs, and interaction terms between treatment and the SNPs.

Safety endpoints are all binary indicators (discontinuation, change of therapy, hyperlipidemia, etc.). All of these safety endpoints will be compared between treatment arms using chi-square tests.

Amendment 6Page 13 of 18

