#### Sample size and power:

The study was powered to measure significant improvements in renal function. To estimate the required sample size we assumed that the estimated glomerular filtration rate (eGFR) would improve from 34 mL/min/1.73 m^2 to 43 mL/min/1.73 m^2 as reported in a recent study by Fairbanks et al [29]. This is a conservative estimate since the renal sparing effects of everolimus are larger than those of sirolimus. A sample size of 12 in each group will have 80% power to detect a difference in means of -9.0 (the difference between a Group 1 mean of 34.0 and a Group 2 mean of 43.0) assuming that the common standard deviation is 7.5 using a two group t-test with a 0.050 two-sided significance level. Fairbanks did not report standard deviations for eGFR, however, a simulation study suggests that the standard deviation at baseline was 7.5, and the standard deviation following conversion was 16. We therefore, considered the sample size requirement for a range of standard deviations, shown in the Figure below. If the common standard deviation was 16, then 51 patients per group would be required to detect a significant difference of 9.0 with 80% power. This sample size may not be feasible for a pilot study such as this. However, 12 per group is feasible and can be justified by the lower limit of standard deviation reported in Fairbanks.

IRB # 38115 Version: December 28, 2018

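### No primary visit is named for creatinine clearance, and the 80% power does not allow for the plan's own Bonferroni rule if several visits are tested

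*Combined protocol and SAP*

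**What the plan says.** Section 11.0 opens with "The primary endpoint of the trial is a renal function as assessed by 24 hour creatinine clearance" and continues "We will compare creatinine clearance between the two arms of the study using a t-test". Neither sentence gives a time point. Section 2.0 gives none for the primary objective either; its 6, 12 and 24 month list belongs to the secondary objectives on survival and rejection.

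The evaluation schedule in Section 6.0 has three follow-up visits: "Visit window for follow up visits at months 6, 12 and 24 is plus or minus 2 weeks". The tests attached to that schedule include "24 hour urine collection for creatinine clearance and urinary protein level starting at Baseline visit". The primary variable is therefore available three times after baseline.

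Two sentences later in Section 11.0 govern significance. The default is "For all statistical analyses we will define significance as p-values less than 0.05". A conditional rule follows. It applies only where more than one comparison is needed, and its example and remedy read "to study the same variable at difference time points) then we will adjust the p-values using a Bonferroni correction". Under the sample size heading, 12 per group is said to give 80% power for a difference of 9.0 with SD 7.5, "using a two group t-test with a 0.050 two-sided significance level".

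**The concern.** A primary t-test cannot be carried out until someone decides which of the three follow-up measurements goes into it. The plan does not decide, and the two obvious ways of settling it later each have a cost.

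- **Test every visit.** This is the example the plan gives for Bonferroni. Each test then has a stricter threshold than the 0.05 used for the sample size, so the stated power no longer describes the test performed.
- **Pick one visit afterwards.** The trial is open label, so a visit chosen once results are visible and tested at 0.05 does not hold the 5% error rate.

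The visits are also not interchangeable. Section 7.0 times the final visit from transplant. If Month 6 is on the same clock, it falls only two to three months after randomization, so the choice of visit changes how much time off the calcineurin inhibitor is being evaluated.

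**Working it through.** **Inputs.** From the sample size paragraph of Section 11.0: n = 12 per arm, difference 9.0 (34.0 versus 43.0), SD 7.5 (alternative 16), two-sided alpha 0.05. From Section 6.0: three follow-up visits. The documents give no between-visit correlation; 0.5 to 0.9 is assumed below.

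**1. The plan's own figure.** Exact power of the two-group t-test, df = 2 × 12 − 2 = 22, noncentrality = 9 / (7.5 × √(2/12)) = 2.94. At alpha 0.05 the critical value is 2.074 and power is **80.2%**, so the stated 80% reproduces. The plan's other figure also reproduces: SD 16 with 51 per group gives 80.3%.

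**2. Same test under Bonferroni.** Only the critical value changes.

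| Visits tested | Alpha per visit | Critical t | Power per visit, SD 7.5 | Power per visit, SD 16 |
|---|---|---|---|---|
| 1 | 0.05 | 2.074 | 80.2% | 26.1% |
| 2 | 0.025 | 2.405 | 70.1% | 17.4% |
| 3 | 0.0167 | 2.591 | 63.8% | 13.5% |

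With three visits and SD 7.5, the difference detectable with 80% power at a given visit rises from 9.0 to about 10.6. Restoring 80% per-visit power for a difference of 9.0 takes 17 per arm (15 with two visits).

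**3. Per-visit power is not trial power.** Simulation with 12 per arm, SD 7.5, a difference of 9 at every visit, equal correlation between visits, and three tests at 0.0167:

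| Correlation | Significant at one or more visits | Significant at all three |
|---|---|---|
| 0.5 | 87% | 38% |
| 0.7 | 82% | 44% |
| 0.9 | 74% | 53% |

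At correlation 1.0 both columns equal 64%.

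**4. Choosing the visit afterwards.** Same simulation with no true difference, the most favourable of three visits tested at 0.05: type I error about 13% at correlation 0.5, 11% at 0.7 and 8.5% at 0.9.

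**5. Timing of Month 6, if counted from transplant.** Month 6 is about day 183. Randomization is at day 90 to 120, so Month 6 is about 183 − 120 = 63 to 183 − 90 = 93 days after randomization, or 49 to 107 days with the two-week window. Section 6.0 sets a reduced calcineurin inhibitor trough as the target by three weeks after randomization, with elimination starting only once that is reached. This enters none of the power figures, which assume the full difference of 9 at every visit.

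**The case against.** The best defence is that the pieces fit together. The primary comparison is described in the singular, the default threshold is 0.05, the sample size assumes one test at 0.05, and the Bonferroni rule applies only if several comparisons are made. With one visit tested, nothing conflicts. This stands. A reader might infer that two rules contradict each other and that the trial's power is really 64%; the documents support neither inference. The rule is conditional, no sentence says that creatinine clearance will be tested at all three visits, and the divisor of three comes from a collection schedule. The 64% is also power at one given visit. If a win at any visit counted, power would be about 74% to 87% over the assumed correlations, and if all three were needed, about 38% to 53%.

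It can also be said that this is a pilot, and that the plan already admits 51 per group would be needed at SD 16. At that SD, power is 26% before any adjustment, so the SD is the larger threat to power. That is correct, but Section 3.0 describes the aim as assessing superiority and Section 11.0 claims 80% power, so the test behind the claim still has to be identified.

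Finally, this version is dated December 2018 and Section 6.0 gives a study end of 1 October 2019. Naming a visit that late invites the charge of post hoc selection. This stands too, and the fix has to meet it.

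What the defence does not supply is the visit. Reading the plan as a single test leaves that test undefined.

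**Conclusion.** The concern holds in a conditional form. The primary analysis lacks a time point, and the power statement is valid only if a single visit is tested alone at 0.05. If all three follow-up visits are tested under the plan's multiplicity rule, power at a given visit falls from 80% to about 64% at SD 7.5, and to 70% with two visits; the sample size paragraph does not account for this. If the most favourable visit is selected after the data are seen and tested at 0.05, type I error is about 8.5% to 13%.

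The power figures rest on the plan's difference of 9 and SD of 7.5, with no dropout. The type I error range, and the any-visit and all-visit powers, also rest on assumed between-visit correlations of 0.5 to 0.9.

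**What to change.** In Section 11.0, name one visit, for example Month 12, at which creatinine clearance is compared between arms, tested alone at two-sided 0.05. Record when and by whom (by role) the choice was made, and that it preceded any between-arm comparison of creatinine clearance. If such a comparison has already been made, say so. Report the other visits as supportive estimates with 95% confidence intervals and no significance claim. The stated 80% then belongs to the planned test on the plan's own assumptions, with no added patients.

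If several visits are to stay primary, state how many comparisons are counted and whether success means significance at a given visit, at any visit or at all of them, and restate the power for that rule. With three comparisons, 64% should be labelled as per-visit power; 80% per visit would need 17 per arm.

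The cost is a short addition to Section 11.0 and the record of its timing. The downside of the single-visit option is that the other two visits lose confirmatory status.

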# 4.0 Inclusion and Exclusion Criteria

Study Population: This will be a pilot study which will include 12 adult deceased donor liver transplant recipients in each study arm.

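### Single-step Bonferroni is valid, but Holm's step-down procedure keeps the same 5% family-wise limit and never rejects less; the gain is modest and depends heavily on the SD

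*Combined protocol and SAP*

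**What the plan says.** The multiplicity rule is in section 11.0, just before the sample-size paragraph. The general threshold is "For all statistical analyses we will define significance as p-values less than 0.05". The adjustment is conditional, and its trigger is worded as follows: "If multiple comparisons are required (for example, to study the same variable at difference time points". The remedy named for that case is the single-step one: "then we will adjust the p-values using a Bonferroni correction". The number of comparisons is not fixed, and no step-down, hierarchical or gatekeeping method appears anywhere.

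The endpoint most likely to be compared repeatedly is the primary one: "The primary endpoint of the trial is a renal function as assessed by 24 hour creatinine clearance". No time point is attached to it. The evaluation schedule in section 6.0 has three post-baseline visits, at months 6, 12 and 24.

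The sample-size paragraph uses one unadjusted test: "A sample size of 12 in each group will have 80% power to detect a difference in means of -9.0". The conditions attached to that figure are these: "assuming that the common standard deviation is 7.5 using a two group t-test with a 0.050 two-sided significance level". It also gives a less favourable case: "If the common standard deviation was 16, then 51 patients per group would be required to detect a significant difference of 9.0 with 80% power". It attributes the SD of 7.5 to baseline and the SD of 16 to the period after conversion. Section 4.0 fixes "12 adult deceased donor liver transplant recipients in each study arm".

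**The concern.** Single-step Bonferroni multiplies every p-value in the family by the number of comparisons. Holm multiplies the smallest by the full number, the next by one fewer, and so on, stopping at the first that fails. Holm's adjusted p-values are therefore never larger than Bonferroni's, and the family-wise guarantee is the same. The usual reason for keeping the single-step version is that it gives simple simultaneous confidence intervals. This plan describes none; it adjusts p-values only.

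What is at stake is the second and later rejections. Once one visit is significant, Bonferroni still holds the others to the full penalty. With 24 patients, a sample size based on an unadjusted 0.05, and no replacement of patients withdrawn after randomization (section 10.0), the plan has little power to spare.

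**Working it through.** **Inputs from the documents.** 12 per arm; difference 9.0; SD 7.5 or 16; two-sided 0.05; two-group t-test (section 11.0). Three follow-up visits (section 6.0).

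**Assumptions not in the documents.** The family is exactly these three visits (m = 3). The difference and SD are the same at each visit. Correlation between visits is equal, at 0.3, 0.6 or 0.8 (some checks used 0, 0.5 and 0.8). There is no dropout.

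**Step 1: the plan's own figures.** The noncentrality is difference / (SD × √(2/n)), with 2n − 2 degrees of freedom.
- SD 7.5, n = 12: 9 / (7.5 × √(2/12)) = 2.94, giving power 80.2%. The stated 80% is reproduced.
- SD 16, n = 51: 9 / (16 × √(2/51)) = 2.84, giving power 80.3%. The stated 51 per group is reproduced.

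**Step 2: thresholds.** For m = 3, Bonferroni requires p ≤ 0.05/3 = 0.0167 at every visit. Holm requires 0.0167 for the smallest p-value, then 0.05/2 = 0.025, then 0.05. The first threshold is the same, so the chance of at least one rejection must be the same.

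**Step 3: exact single-test power at 12 per arm.**

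| Threshold | SD 7.5 | SD 16 |
|---|---|---|
| 0.05 | 80.2% | 26.1% |
| 0.025 | 70.1% | 17.4% |
| 0.0167 | 63.8% | 13.5% |

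Holm's power at a given visit must lie between the bottom and top rows. It cannot exceed the unadjusted 80.2%. Under Bonferroni over three visits, 17 per arm would be needed for 80% at each visit.

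**Step 4: simulation.** 100,000 trials per setting, difference 9.0 at all three visits.

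| SD | Correlation | Given visit: Bonferroni | Given visit: Holm |
|---|---|---|---|
| 7.5 | 0.3 | 64% | 73% |
| 7.5 | 0.6 | 64% | 72% |
| 7.5 | 0.8 | 64% | 71% |
| 16 | 0.3 to 0.8 | about 13.5% | 15-17% |

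The chance of at least one significant visit is identical for the two methods: 91%, 84% and 78% at SD 7.5 for correlations 0.3, 0.6 and 0.8, and 23% at SD 16 with correlation 0.8. In no simulated trial did Bonferroni reject where Holm did not.

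**Step 5: effect at fewer visits (SD 7.5).** With a difference at one visit only, Holm adds about 0.2 point or less at that visit. With a difference at two visits, power at each goes from about 64% to 67-68%.

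**Step 6: error rates.** Suppose k hypotheses are truly null. When Holm first rejects one of them, the threshold is at most 0.05/k. That event has probability at most k × 0.05/k = 0.05, whatever the correlation. The simulations agree (correlations 0, 0.5 and 0.8, SD 7.5):
- No effect anywhere: family-wise error 4.9%, 4.5% and 3.6%, the same for both methods.
- Effect at one visit: error at each null visit rises from about 1.7% to 2.2-2.4%. Family-wise error rises from 2.8-3.3% to 3.5-4.4%.
- Effect at two visits: error at the remaining null visit rises from 1.7% to about 3.5%.

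**The case against.** The strongest reply is that nothing here is wrong. Bonferroni controls the family-wise error, and preferring another valid method is a refinement. That stands.

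The rule may also never touch the primary test. It is conditional, section 11.0 describes a single t-test of creatinine clearance, and the power calculation is for one test at 0.05. If one visit were named primary, the two methods would coincide for it. This also stands: the three-visit family is an assumption, and defining the family matters more than choosing between the two corrections.

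The SD of 7.5 is the favourable case. The plan links 7.5 to baseline and 16 to the period after conversion, and the visits being tested come after conversion. At SD 16 the gain is about 2-3 points per visit. An equal, full effect at every visit likewise favours Holm.

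A reader might go further and infer that Bonferroni throws power away for nothing, pointing to the chance that all three visits are significant: 41% against 60% at SD 7.5 and correlation 0.6. The documents do not support that reading. No objective or analysis requires significance at every visit, and a claim that did would need no multiplicity adjustment at all, because each test could be run at 0.05. At SD 16 the same comparison is 3% against 8%. Nor is Holm free of cost. Bonferroni lets month 6 be judged before month 24 data exist and converts readily to simultaneous intervals, and Holm raises the error at an individual null visit (step 6).

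None of this makes Bonferroni the better choice for adjusted p-values reported together at the end. It limits how much the change is worth.

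**Conclusion.** The point holds as a minor inefficiency. For any fixed family analysed once its results are complete, Holm gives the same 5% family-wise guarantee and rejects at least as often. Under the assumptions listed, the gain at a given visit is about 7 to 9 points at SD 7.5 (64% to 71-73%) and about 2 to 3 points at SD 16 (13.5% to 15-17%). It is close to nothing if the effect is confined to one visit.

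Two inferences should be avoided. Holm does not improve the chance of at least one significant visit, and it does not bring the trial back to the 80% power planned for a single unadjusted test. Dropout, for which the plan makes no allowance, would lower both methods' power below the figures here.

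**What to change.** In the multiplicity sentence of section 11.0, replace "then we will adjust the p-values using a Bonferroni correction" with: *then we will adjust the p-values using Holm's step-down procedure, applied once all p-values in the stated family are available*. State the family in the same sentence, for example creatinine clearance at months 6, 12 and 24, since Holm, like Bonferroni, needs a fixed number of comparisons. Make the change before between-arm results are examined.

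The cost in work is one sentence and a standard software option, with no extra data or patients. The cost in method is threefold:
- No visit can be declared finally non-significant until the family is complete.
- Simple simultaneous intervals are given up, although the plan describes none.
- The false-positive rate at a single null visit rises (about 1.7% to 2.2-2.4% when one other visit has an effect) while the family-wise rate stays under 5%.

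If the sponsor wants to report each visit finally as it completes, keeping Bonferroni is defensible and the plan should say so.
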